7.7 Molecular Complete Response (MCR)

- 7.7.1 For subjects with clonal immunoglobulin heavy chain gene rearrangement, or Bcl2/IgH rearrangement by PCR, MCR will be defined as the inability to detect a previously detectable malignant clonal population of cells using a PCR-based assay on bone marrow and/or peripheral blood specimens.

7.8 Response Rates

- 7.8.1 ***Response to Lenalidomide with and without Dexamethasone:*** Response rate is defined as the percentage of subjects who attain complete response (CR), complete response unconfirmed (CRu), or partial response (PR) after two cycles of –study treatment (lenalidomide-dexamethasone for Cohort 1 subjects; lenalidomide monotherapy for Cohort 2 subjects. Subjects may be scored as having progressive disease (PD) after 2 cycles of –study treatment and will be removed from the study if the estimated life expectancy is < 3 months at that time. Following an intent-to-treat analysis plan, all subjects who receive one day of chemotherapy will be included in the denominator for this response rate.
- 7.8.2 ***Response to Lenalidomide + Rituximab with and without Dexamethasone:*** Response to lenalidomide plus rituximab with and without dexamethasone is defined as the percentage of subjects in complete remission (CR), complete remission unconfirmed (CRu), partial response (PR), or with stable disease (SD) at the 3 months post-rituximab evaluation. Only subjects who receive rituximab are included in the denominator for this secondary response rate.

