To study the immunomodulatory effect of lenalidomide, as well as its possible role in host-associated rituximab resistance, we will analyze changes in peripheral blood mononuclear cells (PBMC) constitution (e.g., changes in NK cell, activated NK cell, activated T cell and Treg numbers) following exposure to lenalidomide and correlate various cell subtype levels and changes to the objective response rates to therapy with rituximab + lenalidomide with and without dexamethasone, compared to Part I with lenalidomide with and without dexamethasone alone. In addition, plasma samples both pre- and post-therapy will be tested for changes in plasma cytokines (i.e., interferon-gamma, GM-CSF, sIL-2R, IL-2, IL-10, IL-12, Rantes) in an attempt to correlate anti-tumor activity to lenalidomide-associated immunomodulatory effects on these cytokines. It is hypothesized that at least some of the immunomodulatory effects of lenalidomide may be mediated through the release of immunostimulatory cytokines. The proposed correlative studies seek to assay plasma cytokine levels pre- and post-therapy and correlate values with clinical outcome.

2 Study Objectives

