2.1 Primary Objectives

- 2.1.1 To determine the response rate to lenalidomide + rituximab therapy with and without dexamethasone in relapsed small B-cell lymphomas with rituximab resistance.

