2.2 Secondary Objectives

- 2.2.1 To determine time to progression after lenalidomide + rituximab therapy with and without dexamethasone in relapsed small B-cell lymphomas with rituximab resistance and compare the time to progression for the previous rituximab-containing regimen
- 2.2.2 To compare the response rate for the previous rituximab-containing regimen to that obtained subsequently to lenalidomide + rituximab therapy with and without dexamethasone.
- 2.2.3 To determine the toxicity profile of lenalidomide + rituximab therapy with and without dexamethasone in patients who have received a previous rituximab-containing combination regimen.
- 2.2.4 To correlate Fc γ RIIIa receptor polymorphism profiling with response to lenalidomide - dexamethasone + rituximab therapy in relapsed small B-cell lymphomas with rituximab resistance (Cohort 1 only).
- 2.2.5 To evaluate changes in NK cells, activated NK cells, activated T cells, T regs, and several plasma cytokines following exposure to lenalidomide - dexamethasone and lenalidomide - dexamethasone + rituximab therapy and correlation of observed changes to objective response rates.

[figure not shown]
2.2.6 To determine the presence or absence of minimal residual disease after Part I and Part II of protocol therapy using a PCR-based assay of DNA.

2.2.7 To determine whether 1) a decrease in serum albumin by ≥ 0.3 g/dL at commencement of cycle 2 from baseline predicts a response (CR/PR) to protocol therapy and whether 2) a baseline serum albumin ≤ 4.1 g/dL predicts no response (SD/PD) to protocol therapy.

3 Study Design

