4.4 Early Withdrawal of Subjects

Subjects will be removed from protocol for any of the following reasons:

[figure not shown]
- Any clinical adverse event, laboratory abnormality or inter-current illness, which, in the opinion of the investigator, indicates that, continued treatment with study therapy is not in the best interest of the subject.
- Any toxicity requiring discontinuation as outlined in the dose modifications criteria in Table 2, Section 6.1.3.
- The subject declines further therapy.
- The subject experiences progression of disease after the first 2 cycles of study treatment (Part I) with estimated life expectancy < 3 months or relapse of lymphoma/progression of disease after having received rituximab (see also Section 7).
- It is deemed in the best interest of the subject. In this instance, the Principal Investigator should be notified.
- Termination of the study by the supporter, Celgene.
- Pregnancy
- The reason(s) for withdrawal should be noted in the case report form and in the subject's medical record. Survival data on patients that withdraw from the trial will be recorded. Statistical analysis will be performed on an intent-to-treat basis.

5 Drug Formulation, Availability and Preparation

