Desquamating (blistering) rash- any Grade	
 Discontinue lenalidomide. Remove patient from study. 	
 Discontinue lenalidomide. Remove patient from study.

Table 2: Lenalidomide Dose Modifications

NCI CTC Toxicity Grade	Onset Day 2-21 of Cycle	Onset \geq Day 22 of Cycle
Neuropathy Grade 3	
 Hold (interrupt) lenalidomide dose. Follow at least weekly. If the toxicity resolves to \leq grade 1 prior to Day 21, restart lenalidomide at next lower dose level and continue the cycle through Day 28. 	
 Omit lenalidomide for the remainder of the cycle. See Instructions for Initiation of a New Cycle and reduce the dose of lenalidomide by 1 dose level.
Grade 4	
 Discontinue lenalidomide. Remove patient from study. 	
 Discontinue lenalidomide. Remove patient from study.
Venous thrombosis/embolism \geq Grade 3	
 Hold (interrupt) lenalidomide and start anticoagulation; restart lenalidomide at investigator's discretion (maintain dose level). 	
 Omit lenalidomide for remainder of cycle.
Hyperthyroidism or hypothyroidism	
 Omit lenalidomide for remainder of cycle, evaluate etiology, and initiate appropriate therapy. See Instructions for Initiation of a New Cycle and reduce the dose of lenalidomide by 1 dose level. 	
 Omit lenalidomide for remainder of cycle, evaluate etiology, and initiate appropriate therapy. See Instructions for Initiation of a New Cycle and reduce the dose of lenalidomide by 1 dose level.
other non-hematologic toxicity \geq Grade 3 attributable to lenalidomide	
 Hold (interrupt) lenalidomide dose. Follow at least weekly. If the toxicity resolves to \leq grade 2 prior to Day 21, restart lenalidomide at next lower dose level and continue the cycle through Day 28. 	
 Omit lenalidomide for remainder of cycle. See Instructions for Initiation of a New Cycle and reduce the dose of lenalidomide by 1 dose level.

NOTE: If subjects do not have adequate hematological recovery within 28 days of their last study treatment, lenalidomide will be discontinued and not restarted. However, the subjects will still be followed for response assessment and included in endpoint analyses.

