7.4 Stable Disease (SD)

7.4.1 Stable disease is defined as less than a PR (see above) but is not progressive disease (see below).

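### Section 7.8.2, the only Section 7 definition that fits primary objective 2.1.1, counts stable disease as response, calls itself secondary, and leaves the denominator for 2.1.1 unsettled

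*Combined protocol and SAP*

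**What the plan says.** The primary objective (2.1.1) reads: "To determine the response rate to lenalidomide + rituximab therapy with and without dexamethasone". Section 7.8 then gives two response rates.

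- **7.8.1** (Part I, before rituximab) counts CR, CRu and PR. Its denominator is intent-to-treat: everyone with at least one day of treatment.
- **7.8.2** (lenalidomide + rituximab) counts CR, CRu, "partial response (PR), or with stable disease (SD) at the 3 months post-rituximab evaluation". On the denominator it says: "Only subjects who receive rituximab are included in the denominator for this secondary response rate".

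Other places bear on what counts as response:

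- 7.4: "Stable disease is defined as less than a PR (see above) but is not progressive disease".
- Objective 2.2.7 takes response to protocol therapy as CR/PR and asks whether low baseline albumin "predicts no response (SD/PD) to protocol therapy". The albumin paragraph of section 8 uses the same split.
- 1.4 speaks of "objective response rates to therapy with rituximab + lenalidomide".
- 4.1 admits patients whose earlier rituximab gave less than a PR, or who progressed within 6 months of a dose.

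On analysis sets, 4.4 says: "Statistical analysis will be performed on an intent-to-treat basis". Section 8 puts all subjects in the intent-to-treat analysis, but also makes anyone who does not complete rituximab non-evaluable and replaceable.

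**The concern.** There are three linked problems.

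**Numerator.** A patient with stable disease is a responder under 7.8.2 and a non-responder under 7.8.1, 2.2.7 and the albumin analysis. The same outcome on earlier rituximab helps qualify the patient for the trial as rituximab-resistant.

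**Label.** 7.8.2 describes the combination that 2.1.1 makes primary, yet calls its rate secondary. If the label is right, Section 7 has no definition written for the primary objective. If the label is a slip, the primary definition is the one that counts SD.

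**Denominator.** Three sets compete: all subjects (intent-to-treat), rituximab recipients (7.8.2) and rituximab completers with replacement (section 8). None is tied to 2.1.1.

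Two analysts working faithfully from this text could therefore report different primary rates from the same data. The rate taken from 7.8.2 would be the higher one whenever any treated subject has SD or any subject with no response never receives rituximab.

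**Working it through.** **1. The plan's own power figure.** Section 8 gives 87% power for McNemar's test with response rates of 10% (baseline) and 35% (study), kappa 0.10 and n = 45. Its alpha is not stated for this test; I assume two-sided 0.05, as in the albumin analysis.

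- Chance agreement: 0.10 × 0.35 + 0.90 × 0.65 = 0.620.
- Agreement at kappa 0.10: 0.620 + 0.10 × (1 − 0.620) = 0.658, so the discordant share is 0.342.
- Discordant cells: (0.342 + 0.25)/2 = 0.296 and (0.342 − 0.25)/2 = 0.046.
- Enumerating the number of discordant pairs gives 87.3% for the uncorrected test (81.7% for the exact test).

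The 87% reproduces. It depends on the assumed 10% and 35%, not on the wording of 7.8.2.

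**2. Definitions side by side.**

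| Place | SD counts as | Denominator |
|---|---|---|
| 7.8.1 | not response | at least one day of treatment |
| 7.8.2 | response | received rituximab |
| 2.2.7 and section 8, albumin | no response | not stated |
| 4.1, prior rituximab | failure (less than PR) | not applicable |
| 4.4; section 8, intent-to-treat | not stated | all subjects |
| section 8, evaluable | not stated | completed rituximab; others may be replaced |

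**3. Size of the SD effect.** The counts are assumptions. I take 45 rituximab-treated subjects and 16 with CR/CRu/PR, the whole number closest to the plan's 35%. The 7.8.2 rate is (16 + SD)/45.

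- SD = 0: 16/45 = 35.6% (exact 95% CI 21.9 to 51.2%).
- SD = 5: 21/45 = 46.7%, or +11.1 points.
- SD = 10: 26/45 = 57.8%, or +22.2 points.

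For scale, section 8 promises a confidence-interval half-width of at most 15 points for any response fraction. Ten SD would shift the estimate by more than that.

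**4. Size of the denominator effect.** Suppose 5 further subjects start therapy, never receive rituximab and count as non-responders. The CR/CRu/PR rate is then 16/50 = 32.0%, against 35.6% on rituximab recipients, a difference of 3.6 points. With both effects (10 SD and 5 never treated) the comparison is 57.8% against 32.0%, a gap of 25.8 points.

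**5. A check against the plan's early data.** The albumin paragraph reports 8 responders and 3 non-responders in the first eleven patients, beside a CR/PR definition: 8/11 = 72.7% (exact 95% CI 39.0 to 94.0%). SD can be no more than the non-responders. If those eleven were representative and all three non-responders had SD, the SD effect would be at most 3/11 = 27.3 points. It would be less if any had progressed.

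**The case against.** **7.8.2 may be a deliberate secondary rate.** It says it is secondary, and 7.10 likewise treats PFS counted from rituximab as a secondary analysis. On that reading the general intent-to-treat rule governs 2.1.1 and nothing primary is inflated. This stands in part: the inflation is conditional on 7.8.2 being used for 2.1.1. But an intent-to-treat rule does not say whether SD counts, and 2.1.1 would then have no response definition of its own in Section 7.

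**A reader might infer that the plan has no other definition and no analysis set at all.** That goes too far. Objective 2.2.7 and the albumin analysis define response to protocol therapy as CR/PR, and 4.4 and section 8 state intent-to-treat. The fault is that the statements compete.

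**Few subjects may miss rituximab.** After Part I, progression leads to removal only when estimated life expectancy is under 3 months; other patients with progression go on to rituximab. Section 6.1.2 lets patients with cytopenias proceed with rituximab. The note in 6.1.3 that "the subjects will still be followed for response assessment and included in endpoint analyses" does not conflict with 7.8.2 for those who still receive it. This stands: the denominator effect is probably the smaller one, and the plan gives no figure for it.

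**The base case may be too low.** The assumed 35.6% lies below the 39.0% lower limit from the first eleven patients. This also stands. A higher true response rate leaves less room for SD.

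**A reader might infer that McNemar's test is biased or its power wrong.** The documents do not support either. Section 8 does not say that SD counts for that test in either period, and the 87% is sound on its own inputs.

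**Conclusion.** The point holds as a contradiction in the endpoint definition. Section 7.8.2 conflicts with 7.8.1, 7.4, 2.2.7, the albumin analysis and the eligibility rule on whether SD is response. Its label conflicts with 2.1.1, and no denominator is assigned to the primary objective.

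The size is conditional. If 7.8.2 serves 2.1.1, each SD among 45 treated subjects adds 1/45 = 2.2 points. The illustrated 11.1 and 22.2 points rest on assumed counts of 5 and 10; the 3.6 points for the denominator rest on an assumed 5 subjects never given rituximab. The real counts are not in the documents, and SD may be few. It cannot be said that the primary rate will be inflated by any particular amount, or that the trial's overall conclusion turns on it. The wording still needs correcting, because the primary result should not depend on which section an analyst follows.

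**What to change.** Amend 7.8.2 and section 8 as follows.

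- Define response to lenalidomide + rituximab as CR + CRu + PR, and state that this is the primary endpoint for 2.1.1. Remove the secondary label from it.
- Use all subjects who start protocol therapy as the primary denominator. Count those who never receive rituximab, or who have no 3-month post-rituximab evaluation, as non-responders. Align the wording in 4.4, 7.8.1 and section 8 with this set.
- Report the rate among rituximab recipients as supportive, and CR + CRu + PR + SD separately as a disease-control rate.
- State that McNemar's test uses CR + CRu + PR in both periods.

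The cost is a short text amendment, with no change to treatment or visits. The reported rate will be lower than 7.8.2 would give if any subject has SD or any subject with no response never receives rituximab. Some prior-regimen responses may need scoring from source records. The amendment should disclose that it follows the look at the first eleven patients. The 87% power statement needs no correction on this account.

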7.9 Time to progression (TTP)

TTP is defined as the time from the first day of protocol therapy to the first event defining progression of disease or last subject contact. TTP is defined for all subjects receiving protocol therapy, following an intent-to-treat analysis plan. TTP from rituximab is defined for patients receiving rituximab (Part II) from the first day of rituximab therapy to the first event defining treatment failure.

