In Part I of the study, subjects in both cohorts will receive lenalidomide 10 mg PO once daily on Days 1-28 every 28 days for two 28-day cycles. Subjects in Cohort 1 will also receive dexamethasone 8 mg PO once weekly (dosing on Days 3, 10, 17 and 24 is suggested, but not required) for two 28-day cycles. Serum and plasma samples for ancillary studies will be collected for all subjects upon entry into the trial, after 2 cycles of study therapy, and at the investigator's discretion in subjects with extended remissions. Subjects will be restaged after the first 2 cycles (Part I) prior to Part II and will continue with Part II (with rituximab) unless progression of disease is documented with life expectancy estimated to be <3 months during Part I.

In Part II, all subjects will receive lenalidomide once daily Days 1-28 over 28 days as well as Rituximab 375mg/m² IV once weekly during cycle 3. Subjects enrolled in Cohort 1 will also receive dexamethasone PO once weekly during each 28 day treatment cycle. The doses of lenalidomide and dexamethasone (for subjects in Cohort 1) during Part II will be determined by dose modification guidelines in Section 6. All subjects will be restaged 3 months after first rituximab infusion (prior to cycle 6). Again, serum and plasma samples for ancillary studies will be collected at this point. Following Part II, subjects in Cohort 1 will continue on lenalidomide once daily on Days 1-28 every 28 days and dexamethasone once weekly until disease progression, development of unacceptable toxicity, or voluntary withdrawal, whichever occurs first.

Subjects in Cohort 2 will continue on lenalidomide once daily on days 1-28 of each 28 day cycle. Restaging for all subjects will be performed on months 12, 18 and 24 (as counted from enrollment of trial) and then yearly until disease progression, development of unacceptable toxicity, or voluntary withdrawal, whichever occurs first. These restaging assessments may be performed +/- 2 months from these timepoints, or at the clinical discretion of the treating physician.

Subjects are required to receive prophylactic anti-coagulation with aspirin, Coumadin or low molecular weight heparin due to the increased risk of thrombosis reported with lenalidomide therapy. Coumadin should only be used with caution and close monitoring of INR. Prophylactic anti-coagulation should be held for platelet counts $< 50,000/\text{mm}^3$ and restarted when platelet counts are $\geq 50,000/\text{mm}^3$.

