3.3 Table of Events

Tests & Observations (see footnote M)	Prior to study	Prior to starting Cycles 1-6	Restaging after Part I	Restaging after Part II and subsequent follow- up*
History	X			
Physical Examination	X	X	X	X
Height	X			
Weight, BSA**	X		X	
Performance Status	X	X	X	X
Tumor measurements	X	A	X	X
Drug toxicity Assessment		X	X	X,N
Register into Revlimid REMS® program	X,O			
EKG	X			
Laboratory Studies (see footnote M)				
CBC, Differential, Platelets	X	X,H	X	X
Serum Creatinine, BUN	X	X,	X	X
Serum Electrolytes	X	X,	X	X
Total Protein, Albumin	X	X	X	
AST,ALT, Alk. Phos., Bilirubin	X	X	X	X
ESR, CRP, Fibrinogen	X^	X, ^	X^	X,C^
Uric acid/Phosphate/LDH/Ca ⁺⁺	X	X,J	X	X,C
Serum or urine b-HCG***	X, B	B	X	B
Serum IgG, IgA, IgM	X^	X,C^	X^	C^
FCR Polymorphism Sample (see 3.5)	X^			
Blood and Plasma Sample (see 3.5)	X		X	D
HACA				E^
HBsAg, HepCAb, HBcAb	F			F
TSH (repeat only if clinically indicated)	X			
Staging (see footnote M)				
CT / MRI (chest/abd/pelvis) / PET-CT	X		X	X
CT Scan/MRI (neck)	G		G	G
Bone Marrow Asp& BX (unilateral)	P		K	K
Histologic Review	X		L	L

* Follow-up staging on months 12, 18 and 24 as counted from enrollment, then yearly until disease progression, development of unacceptable toxicity, or voluntary withdrawal, whichever occurs first. Physical exams and study labs should be done monthly for the first 6 months, every two months for cycles 7-13 and every three months thereafter (+/- 2 weeks). After the first 6 months of weekly labs, subjects will continue to have a CBC monthly while on-study.

** Although doses are recalculated prior to each treatment, the actual dose of rituximab to be given need not change unless the calculated dose changes by $\geq 10\%$. NOTE THAT LENALIDOMIDE DOSES ARE NOT BASED ON WEIGHT OR BSA.

*** Pregnancy tests for females of childbearing potential. A female of childbearing potential (FCBP) is a sexually mature female who: 1) has not undergone a hysterectomy or bilateral oophorectomy; or 2) has not been naturally postmenopausal for at least 24 consecutive months (i.e., has had menses at any time in the preceding 24 consecutive months).

[^] Subjects enrolled into Cohort 1 only. Not applicable for subjects enrolled into Cohort 2.

A If accessible to physical examination, please record measurements

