7.10 Progression free survival (PFS)

PFS is defined as the time from first day of protocol therapy to disease progression, death due to any cause or last subject contact. PFS is defined for all subjects entered on the study, following an intent-to-treat analysis plan. A secondary analysis will also include a calculation of PFS from day of rituximab infusion.

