7.11 Overall Survival (OS)

Overall survival is defined as the time from first day of protocol therapy to death due to any cause or last subject contact.

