10.2 Confidentiality

Information about study subjects will be kept confidential and managed according to the requirements of the Health Insurance Portability and Accountability Act of 1996 (HIPAA). Those regulations require a signed subject authorization informing the subject of the following:

- What protected health information (PHI) will be collected from subjects in this study
- Who will have access to that information and why
- Who will use or disclose that information
- The rights of a research subject to revoke their authorization for use of their PHI.

In the event that a subject revokes authorization to collect or use PHI, the investigator, by regulation, retains the ability to use all information collected prior to the revocation of subject authorization. For subjects that have revoked authorization to collect or use PHI, attempts should be made to obtain permission to collect at least vital status (i.e. that the subject is alive) at the end of their scheduled study period.

Celgene affirms the subject's right to protection against invasion of privacy. In compliance with United States federal regulations, Celgene requires the Investigator to permit Celgene's representatives and, when necessary, representatives of the FDA or other regulatory authorities to review and/or copy any medical records relevant to the study in accordance with local laws. Should direct access to medical records require a waiver or authorization separate from the subject's statement of informed consent, it is the responsibility of the Investigator to obtain such permission in writing from the appropriate individual.

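### TTP and PFS run to last subject contact, the cut-off used for survival, so time with no disease assessment after a subject leaves can count as progression-free

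*Combined protocol and SAP*

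**What the plan says.** Three endpoints share one cut-off. TTP (7.9) runs to "the first event defining progression of disease or last subject contact". PFS (7.10) runs to "disease progression, death due to any cause or last subject contact". OS (7.11) runs from "first day of protocol therapy to death due to any cause or last subject contact". Contact is not defined, and nothing ties it to a disease assessment.

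Disease assessment and survival follow-up end at different times. Section 3.1 schedules restaging at months 12, 18 and 24 "and then yearly until disease progression, development of unacceptable toxicity, or voluntary withdrawal, whichever occurs first", and the staging footnote in 3.3 agrees. Section 4.4 adds: "Survival data on patients that withdraw from the trial will be recorded". It also makes the analysis intent-to-treat, so subjects who leave remain in TTP and PFS.

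There is one stated exception. The note to Table 2 (6.1.3) keeps subjects whose lenalidomide is stopped for inadequate hematological recovery under response assessment.

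Section 7.9 also defines a second TTP, counted from the first day of rituximab to treatment failure. Section 8 tests the ratio of the median TTP on combination treatment to the median TTP on rituximab alone, without saying which TTP forms the numerator.

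**The concern.** For OS, last contact is the right cut-off, because any contact shows that the subject is alive. For TTP and PFS a contact need not show anything about the lymphoma. If a subject stops treatment for toxicity at month 3 without progression and is then known only to be alive at month 20, 7.9 as written credits 20 progression-free months.

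This matters because the error runs one way. At each recorded progression the Kaplan-Meier factor is 1 - d/n. A later censoring date can only increase n, so with the same events the curve rises or stays put. The study-period median is meant to be compared with the median on the previous regimen (objective 2.2.1), so any such error would favor the study regimen.

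**Working it through.** **Is there a plan figure to reproduce?** No stated figure depends on the cut-off. The only nearby one is the 83% power for medians of 3 and 6 months with 45 subjects. Section 8 gives no TTP distribution, accrual or censoring for it, so it cannot be rebuilt from stated inputs, and this point does not dispute it.

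**Inputs.** From the documents: 45 subjects; restaging after Part I (about month 2), at month 5, then months 12, 18, 24 and yearly; a 6-month median as the Section 8 alternative. Assumed, because the documents are silent: exponential TTP; 4, 7 or 10 of 45 leaving progression-free at a constant rate over months 0-5; contact to month 12 or 24; median survival after leaving of 12 to 36 months; 0, 50 or 80% of later progressions learned.

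**Exact dating, closed form for 7 leavers, none learned.** The progression hazard is λ = ln 2 / 6 = 0.1155. The leaving hazard h solves h/(h+λ) × (1 - e^(-5(h+λ))) = 7/45 = 0.1556, which gives h = 0.0453. If leavers stay in the risk set beyond the median:

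- The progression-free share at month 5 is 1 - λ/(h+λ) × (1 - e^(-5(h+λ))) = 1 - 0.718 × 0.5525 = 0.603. The true value is 2^(-5/6) = 0.561.
- A fraction e^(-5(h+λ)) = 0.4475 is still under assessment at month 5. The median solves 0.603 - 0.4475 × (1 - e^(-λ(t-5))) = 0.5, so t = 5 + 0.262/0.1155 = 7.3 months.

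Letting some leavers die (censored for TTP) brings this to 7.1-7.2 in simulation.

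**Exact dating, simulated median TTP in months (400,000 subjects per setting; truth 6.0).**

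| Leavers of 45 | None learned | Half learned | 80% learned |
|---|---|---|---|
| 4 | 6.5-6.6 | 6.2-6.3 | 6.1 |
| 7 | 7.1-7.2 | 6.5 | 6.2 |
| 10 | 7.8-8.0 | 6.7-6.8 | 6.3 |

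Censoring at the moment of leaving returns 6.0. If contact ends 30 days after leaving, the median is 6.1-6.3 even with none learned. For PFS the rule gives 6.2-7.5 with none learned, because a later death ends the interval. It gives 6.0 if median survival after leaving is only 6 months.

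**Progression dated only at scheduled scans (contact to month 24).** The true shares are 2^(-5/6) = 0.56 at month 5 and 2^(-12/6) = 0.25 at month 12, so the stepped curve first falls below one half at month 12. The median is 12.0 under the rule as written, under censoring at leaving and under censoring at the last scan. Only the curve moves: the month-5 share is 0.57-0.65 as written, against 0.56.

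**Significance test.** True medians were set at 3 and 3 months, with a paired bootstrap interval for the ratio of medians standing in for the planned one (3,000 trials, error about ±0.8 points). The interval excludes 1 in 4.5, 6.2 and 8.3% of trials with 4, 7 and 10 leavers and none learned, in 4.4-4.7% with half learned, and in 3.9-4.1% with 80% learned. Censoring at leaving gives 3.5-4.0%.

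**The case against.** The best case against acting has five parts.

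- *Contact may mean a study visit.* Section 9.2 uses the word for an encounter with questioning and, where appropriate, examination. The reading is possible, but 7.11 uses the same phrase for OS and 4.4 collects survival after withdrawal. If the narrower meaning is intended, the same edit states it.
- *The leaver counts are assumed and may be high.* This stands. The Table 2 note keeps one group under assessment. Section 8 also lets subjects who do not complete rituximab be replaced while staying in the intent-to-treat set. If all 10 leavers were replaced, their share would be 10/55 = 18%, not 10/45 = 22%.
- *Scan spacing is the larger error.* This stands for the median: dated at scans, it does not move. Practice lies between the two cases, since examinations are monthly at first and footnote A of 3.3 asks: "If accessible to physical examination, please record measurements".
- *The tested TTP may be the other one.* This stands. TTP from rituximab excludes anyone who leaves before rituximab, which is about half of the assumed leavers (48-51% go before month 2), and its definition does not mention last contact.
- *Section 10.2 adds little.* Agreed. It describes a vital-status attempt, with permission, for subjects who revoke authorization. The point rests on 4.4.

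**Conclusion.** The point holds as a defect of definition with low importance. As written, 7.9 and 7.10 let unassessed time count as progression-free, and for given events the curve can only rise or stay put. Subjects followed under the Table 2 note, later progressions that are learned, and subjects who leave after the median do not distort the median.

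The size is not determined by the documents. It ranges from no change in the median (scan dating) to about 2 months (10 leavers, none learned, exact dating), all under assumed inputs.

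Three stronger readings are not supported:

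- A reader might infer that the reported median will be overstated by a known amount. The withdrawal rate, length of contact and share of progressions learned are not given.
- A reader might infer that the Section 8 ratio is biased. That follows only if its numerator is TTP from first protocol therapy, which Section 8 does not say.
- A reader might infer that the significance test is broken, since a log-rank comparison with 12 months of unassessed contact and none learned gives false-positive rates of about 15% to 94% at 10% to 40% withdrawal. Section 8 plans an interval for a ratio of medians, not a log-rank test. In the stand-in for that interval, rates exceed 5% only with at least 7 leavers and no progression learned.

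**What to change.** In 7.9 and 7.10, replace the last-contact cut-off with: *last disease assessment (imaging or physical examination with tumor evaluation) showing no progression*. Keep last subject contact for OS in 7.11 only. Add two rules:

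1. Subjects with no post-baseline assessment are censored at day 1.
2. Documented assessments obtained after withdrawal count both ways: as an event if they show progression, and as the censoring date if they do not. Counting only the progressions would pull the median down, to 5.4-5.9 months in the same illustration.

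Section 8 should also say which of the two TTP definitions enters the ratio.

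The cost is one phrase in two sections and a few sentences, with no extra scans or visits. The downside is that median TTP and PFS may look slightly shorter. Under exact dating with no later progression learned, the TTP median reads 5.6-5.9 months if only scans count (up to about 0.4 low) and 5.8-6.0 if monthly examinations count as well.
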